		Appendix 10.9 .

Patients with co-morbidities associated with potentially increased risk to nintedanib will be excluded (see [Section 3.3.3](#)).

An external Safety Monitoring Committee (SMC) will ensure monitoring of safety throughout the conduct of the study. Further details on SMC and other external committees in [Section 7](#).

1.4.3 Discussion

This open label trial only started recruiting once the first results of InPedILD[®] trial have been reviewed and justify the start of this open label trial by confirming that safety and tolerability of nintedanib is considered acceptable in the patient population of the InPedILD[®] trial.

The planned trial procedures and the associated risks are deemed acceptable, as they allow for timely identification of potential risks, interruption or discontinuation of treatment if required to manage adverse events/ adverse drug reactions.

Given the high unmet need for treatment options in paediatric fibrosing ILDs, the established clinical benefit and known safety profile of nintedanib in adults, as well as the expected benefit of nintedanib in the paediatric fibrosing ILD, the extrapolated benefit-risk of nintedanib in the target population is considered acceptable.

2. TRIAL OBJECTIVES AND ENDPOINTS

2.1 MAIN OBJECTIVES, PRIMARY AND SECONDARY ENDPOINTS

2.1.1 Main objectives

The trial will assess the safety and tolerability of long-term treatment with nintedanib in pediatric patients with clinically significant fibrosing ILD.

[figure not shown]
The primary objective is to estimate the incidence of treatment emergent adverse events over the whole trial.

[figure not shown]
2.1.2 Primary endpoint(s)

The primary endpoint is the incidence of treatment emergent adverse events over the whole trial.

2.1.3 Secondary endpoint(s)

No secondary endpoints are defined.

3. DESCRIPTION OF DESIGN AND TRIAL POPULATION

3.1 OVERALL TRIAL DESIGN

This is a multi-centre, multi-national, not randomised, open label clinical trial.

[figure not shown]

Figure 3.1:1 Trial design

The patient population will include two cohorts:

Patients rolling over from the InPedILD[®] study:

At the time point when the data from the InPedILD[®] trial are available, and a positive benefit risk assessment (by external independent SMC and internal BI Benefit Risk Committee) justifies the start of the current trial, all patients on study treatment (including those who temporarily interrupted treatment for less than 8 weeks) at the end of the parent trial InPedILD[®] will be offered participation in the current long-term study. These patients can be enrolled into 1199-0378 from Part A or from Part B.

Patient’s individual benefit-risk to receive long-term treatment of nintedanib should be assessed by the investigator. The decision to participate in this study will be made by the patient/parent(s)/legal guardian following a discussion on this benefit-risk assessment with the investigator.

Completed patients from the parent trial not able to roll-over into the extension trial within 12 weeks following their End of Treatment Visit in the parent trial (i.e. time period between last dose of study drug in parent trial and first dose in extension trial is greater than 12 weeks) will formally not be considered as “roll-over” patient. These patients will be handled as new patients in 1199-0378, i.e. they have to follow the visit schedule for new patients but will have adapted inclusion/exclusion criteria (please refer to [Section 3.3.2](#) and to [Section 3.3.3](#)).

Patients who prematurely permanently discontinued treatment due to AE considered related to nintedanib in the InPedILD[®] trial will not be eligible for this open-label trial.

Patients who permanently discontinued trial treatment due to AE considered related to placebo or for reasons other than drug-related AE and are willing to participate in study 1199-0378 will potentially be eligible for this open-label trial. For those patients, the individual benefit risk and potential eligibility for participation in study 1199-0378 should be carefully assessed by the investigator and should be discussed with the sponsor. These patients will be handled as new patients in 1199-0378, i.e. they have to follow the visit schedule for new patients.

Patients who have withdrawn consent to trial participation in InPedILD[®] will not be eligible for 1199-0378.

Whenever feasible, for roll-over patients, the first visits (Visit 1 and Visit 2) of this open-label trial should be on the same day as the End of Treatment visit of InPedILD[®], the parent trial, to allow for continuous treatment. In this case, procedures performed at the EoT of InPedILD[®] should not be repeated if stated as planned at Visit 1 or Visit 2 in the 1199-0378 trial (please refer to [section 6.2.1](#) and [Flow Chart](#)).

After signing Informed Consent, and if all eligibility criteria are met, patients will receive treatment with nintedanib at their last dose of study medication in the parent trial 150 mg b.i.d. (300 mg daily), 100 mg b.i.d. (200 mg daily), 3x25 mg b.i.d. (150 mg daily), 2x25 mg b.i.d. (100 mg daily) or 25 mg b.i.d. (50 mg daily) unless the patient's weight has changed such that a different dose is required (please refer to [Table 4.1.2: 1](#)).

For those patients with dose reduced in the parent trial, the dose can be increased based on the judgement of the investigator. Similar to the parent trial, dose reduction to the next lower dose is possible to manage adverse events.

At the time point of start of this open label study, the treatment received by the patient in the parent trial in Part A remains blinded until the final DBL (DBL2) occurs for the parent trial.

Patients newly enrolled in the study:

Enrollment will also be open to newly identified children and adolescents with clinically significant fibrosing ILDs if they meet the eligibility criteria of the current protocol, or to patients who needed to discontinue trial treatment (due to AE considered related to placebo or for reason other than drug-related AE) in InPedILD[®] and again are eligible for treatment with nintedanib according to investigator's assessment (and after discussion with the sponsor).

All new patients recruited for the study will enter a 4-week screening period. After this first period, patients meeting in-/exclusion criteria will initiate their treatment period of the study. Starting dose assigned will be based on patient's weight:

150 mg b.i.d. (300 mg daily), 100 mg b.i.d. (200 mg daily), 3x25 mg b.i.d. (150 mg daily), 2x25 mg b.i.d. (100 mg daily).

For all patients, during treatment period, dose is adjusted based on patient's weight. Dose reduction to the next lower dose is possible to manage adverse events. The lowest possible dose is 25 mg b.i.d. (50 mg daily).

Roll-over patients will be requested to stay in the trial for at least 156 weeks (until Visit 15). At week 156, roll-over patients who can be treated with nintedanib or alternative treatment options outside the clinical trial will have their EoT Visit instead of Visit 15.

The remaining roll-over patients will continue in the trial until nintedanib or alternative treatment options can be made available to them outside the clinical trial.

New patients will be requested to stay in the trial until the end of trial (with expected minimum treatment duration of 76 weeks), then patients will perform their EoT Visit and enter in the 28-days follow-up period off-treatment until End of Study Visit (EOS).

Exception: patients aged 21 years must complete the trial before their 22nd birthday. Consequently, a treatment duration of at least 3 years might not be reached by some patients aged 21.

Patients completing trial while being 21 years old, even with a treatment duration less than 3 years, will be considered as completed patients.

The overall end of trial will take place approximately when last roll-over patient is expected to reach 3 years of treatment () ensuring nintedanib or alternative treatment options (e.g., via marketing authorization, via compassionate use, or via similar process) will be available for all remaining patients (roll-over or new patients) outside the trial at this time.

At this time, all the remaining patients will perform their EoT Visit. For logistical reasons, it may be planned that EoT visit of all remaining patients will occur within 6 weeks before the planned date of Visit 15 of last roll-over patient. If regular scheduled visit is planned for a patient during this period of 6 weeks, then the patient will skip this regular visit and will perform directly the EoT visit instead. After the EoT visit, all remaining patients will enter a 4-week follow-up period.

Trial medication will be stopped prematurely if a reason for withdrawal is met (refer to [section 3.3.4](#)).

Roll-over patients will be considered as prematurely discontinued from trial treatment if they stop trial medication before week 156 (except at the age of 21).

New patients will be considered as prematurely discontinued from trial treatment if they discontinue trial treatment before the overall end of trial (except at the age of 21).

Patients who prematurely discontinue trial medication should come to the clinic to perform EoT as soon as possible after treatment discontinuation.

Roll-over patients prematurely discontinued from trial treatment before week 156 will be asked to remain in the study and return to all regularly scheduled visits until Visit 15 (individual planned date of week 156).

New patients prematurely discontinued from trial treatment will be asked to remain in the study until the overall end of trial (expected to occur approximately when last roll-over patient is expected to reach 3 years of treatment).

For patients who prematurely discontinued trial drug and who are unable to complete the scheduled visits, a follow-up (FU) visit should be planned for 28 days after EoT. In addition, every attempt will be made to collect information on vital status, when applicable, at weeks

24, 52, 76, 104, 128 and 156 and for new patients at EoS. These requests will be outlined in the parental-information form and discussed during administration of the informed consent (the same applies to the assent form, where applicable).

If it is intended by a treatment discontinued patient to use available nintedanib outside the trial after trial treatment discontinuation, the patient should directly undergo the EoS visit 28 days after the EOT visit (no vital status will be required for this patient).

A patient will be considered lost to follow-up if the investigator is not able to contact the patient/parent(s)/legal guardian despite multiple attempts. Every effort must be made; at least 2 telephone contacts plus 1 mailing should be documented. The site must notify the clinical monitor prior to designating a patient as lost to follow-up.

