Intermediate lab tests (“a”-Visits) for safety monitoring may be conducted between scheduled visits, as needed at the discretion of the investigator or as recommended by the SMC.

- Blood and urine samples will be collected and submitted to the central laboratory for analysis.

Samples may be collected locally (e.g. by the general practitioner or a nurse). The Investigator or site personnel may give the patient/parent(s)/legal guardian written instructions and procedures to be followed, together with the trial lab kits for the respective ‘a-Visit’ to be used for collecting and shipping samples to the central laboratory (preferable option) or samples may be analysed locally.

Intermediate pregnancy tests

During the treatment period and the follow-up period a pregnancy test must be conducted in all female patients every 4 weeks.

Urine dipstick pregnancy test kits will be provided locally for use between visits when visit intervals are > 4 weeks. Test results must be documented in the patient’s pregnancy test diary card and transferred to the patient’s records at the next site visit.

Treatment period duration

Treatment duration for each patient will be variable.

Roll-over patients will be requested to stay in the trial for at least 156 weeks (until Visit 15). At week 156, roll-over patients who can be treated with nintedanib or alternative treatment options outside the clinical trial will have their EoT Visit. The remaining roll-over patients will continue in the trial until nintedanib or alternative treatment options become available to them outside the clinical trial.

Trial treatment will be stopped prematurely if a reason for withdrawal is met (refer to [Section 3.3.4](#)).

After week 156, if reason for study treatment discontinuation is that nintedanib or alternative treatment options become available for patient outside the clinical trial, then the patient will not be considered as early discontinued for treatment.

New patients will stay in the trial until the overall end of the trial (with expected minimum treatment duration of 76 weeks), then patients will perform the EoT Visit.

End of Treatment Visit

If a patient discontinues the study during a scheduled treatment visit, then the scheduled visit will be replaced by the EoT visit. As consequence, roll-over patients that discontinue trial treatment at week 156 should perform EoT visit instead of Visit 15.

Observations and procedures:

- [REDACTED]

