Section to be changed		Clinical protocol synopsis, section 3.3.2. Inclusion criteria, section 3.3.3. Exclusion criteria
Description of change		Trial population in France is limited to adolescents 12 to 17 years old at Visit 2.
Rationale for change		Harmonisation of the CTP for the transition to EU Clinical Trials Regulation with inclusion of current Local Amendment 1 France requested by French Health Authority (ANSM) and already approved to limit the age groups to be enrolled in France.
Section to be changed		Flowchart footnote 13, Section 1.4.2. Table 1.4.2:1 overview of trial related risks, Section 5.2.3. Safety laboratory parameters, Section 6.2.2. treatment period(s), Section 10.9 Visit modification in exceptional circumstances– Table 10.9:1 Modification to visit procedures in exceptional

		circumstances
Description of change		Pregnancy testing will be done every 4 weeks for female patients in Poland and in Norway.
Rationale for change		Harmonisation of the CTP for the transition to EU Clinical Trials Regulation with inclusion of current Local Amendment 1 Poland (requested by Polish Authorities and already approved) and current local amendment 1 Norway (requested by the Norwegian Medicines Agency and already approved).
Section to be changed		Flow Chart:V3a and footnote 4
Description of change		For new patients in Norway, the Visit 3a is also applicable and should be performed at Week 6 (Day 43).
Rationale for change		Harmonisation of the CTP for the transition to EU Clinical Trials Regulation with inclusion of current Local Amendment 1 Norway requested and already approved by the Norwegian Medicines Agency.
Section to be changed		Flow Chart V12 - End of study
Description of change		V12 should be performed at Day 813 +/- 7 days V13 should be performed at Day 897 +/- 7 days V14 should be performed at Day 981 +/- 7 days V15 should be performed at Day 1093 +/- 7 days VX should be performed at Day 1093 +Q84 with time window of +/- 7 days
Rationale for change		Correction of calculation (1 day was missing)
Section to be changed		Flow chart – footnote 25 and Section 6.2.2 treatment period(s) – follow-up visit
Description of change		Sentences added: If the EoT visit has been delayed and has been done 28 days or more after the treatment discontinuation, the follow-up (FU) visit can be skipped.
Rationale for change		To limit the burden for the patient

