$$\text{Sum of all treatment interruption durations [days]}$$

Total dose [g] will be calculated as

$$\text{Sum of durations of exposure on } x \text{ g [days]} * 2 * x \text{ g,}$$

with x in 0.025, 0.05, 0.075, 0.1, 0.15 and summarised as continuous variable.

Dose intensity [%] will be calculated as the amount of drug actually administered divided by the amount of drug that would have been administered, i.e. dose xx mg bid (depending on the body weight) during the planned treatment period (or until study discontinuation), multiplied by 100%. Dose intensity will be summarised as continuous variable and in categories [%]:

- ≤ 30
- > 30 to 50
- > 50 to 90
- > 90 to < 100
- ≥ 100

Exposure-related time-to-event analyses will be performed for the following items:

- Time to first dose reduction (not due to weight-based adjustment) [days]^[1]
- Time to first treatment interruption [days]
- Time to premature treatment discontinuation [days]

^[1] Will only be calculated for patients who started the trial on full dose according to their weight bin at baseline.

Time-to-event [days] for exposure-related analyses is derived based on first trial drug intake as

$$\text{Date of event/censoring} - \text{Date of first trial drug intake [days]} + 1 \text{ day}$$

For the above mentioned time-to-event analyses patients with no such event occurred during the trial will be censored according to the mechanism for censoring as described in [Table 5.4.3: 1](#).

Table 5.4.3: 1 Censoring rules for exposure-related time-to-event analyses

Rule #	Situation	Outcome (Event/Censored)	Date of event/censoring
1	Patient had a documented event and the date of the event is known	Event	Earliest date of event
2	Patient had a documented event and the date of the event is unknown	Event	Imputed date of event (as defined in Section 6.6.3.3)
3	Patient had no documented event and already terminated trial drug (last intake on End of treatment eCRF page available)	Censored	Date of last trial drug intake
4	Patient neither had a documented event nor terminated trial drug permanently (only applicable for potential interim analyses)	Censored	Date of interim data snapshot

These times will also be summarised in categories [weeks] as defined for duration of exposure [weeks] above.

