7.1 DEMOGRAPHIC AND OTHER BASELINE CHARACTERISTICS

Only descriptive statistics are planned for this section of the report.

A table in the CTR will present the number of patients screened, entered and treated. The number of patients prematurely discontinuing trial medication will be shown with the treatment discontinuation decisions as well as primary reasons for discontinuation. The number and percent of patients completing the planned treatment period and the number of patients with treatment ongoing (only applicable for potential interim analyses) will also be presented. Where percentages are shown, the denominator will be the number of patients treated in each patient group.

Descriptive statistics as well as frequency counts will be provided for all demographic and baseline characteristics depicted in [Section 5.4.1](#). The CTR tables will show the relevant descriptive statistics (number and percent within categories; other descriptive statistics for continuous variables) by patient group.

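### Read literally, the week-156 rule counts roll-over patients stopped at an optional, sponsor-scheduled common end of treatment as premature discontinuations

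*Protocol*

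**What the plan says.** Protocol Section 3.1 ends the trial at about the time the last roll-over patient is expected to reach 3 years of treatment, when all remaining patients have their EoT visit. As an option, for logistical reasons, it allows that the "EoT visit of all remaining patients will occur within 6 weeks before the planned date of Visit 15 of last roll-over patient". A regular visit due in that period is replaced by the EoT visit. It then states: "After the EoT visit, all remaining patients will enter a 4-week follow-up period".

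Section 3.1 goes on to say two things about premature stopping.

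- By reason: "Trial medication will be stopped prematurely if a reason for withdrawal is met", with a pointer to Section 3.3.4.
- By time: roll-over patients are considered "prematurely discontinued from trial treatment if they stop trial medication before week 156 (except at the age of 21"). Patients who leave at 21 are expressly called completers. For new patients the boundary is the overall end of trial, not a fixed week. Premature roll-over stops are asked to keep attending visits until their own planned Visit 15.

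Section 6.2.2 adds that if a patient stops after week 156 because nintedanib or an alternative has become available outside the trial, "then the patient will not be considered as early discontinued for treatment".

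SAP Section 7.1 tabulates premature discontinuations with their reasons and also reports this: "The number and percent of patients completing the planned treatment period". SAP Section 5.4.3 lists "Time to premature treatment discontinuation [days"] among the exposure analyses, and Section 7.7 takes its median and quartiles from the Kaplan-Meier curve. The SAP text available does not define what makes a stop premature.

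**The concern.** The time-based rule and the common EoT meet in the same section without a bridge. One planned early exit (age 21) is exempted by name. The other (the common EoT) is not, so the rule reads as covering it.

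At stake is the meaning of two descriptive tolerability outputs. Administrative stops made for the sponsor's convenience would be added to the count of patients who gave up treatment, and would appear as a late cluster of events between weeks 150 and 156. Results are shown by patient group. The effect would fall on roll-over patients only, because for new patients Section 3.1 places the common EoT at the overall end of trial, which is their own boundary.

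**Working it through.** **1. Reproduce the plan's own figure.** Visit 15 is week 156. Day = 7 × week + 1 = 7 × 156 + 1 = 1093, as in the protocol flow chart, with a window of ±7 days (Day 1086 to 1100).

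**2. Earliest common EoT for the last roll-over patient.** 1093 − 6 × 7 = Day 1051, and (1051 − 1)/7 = week 150. The Visit 15 window opens at Day 1086, so the gap is 1086 − 1051 = 35 days. The visit tolerance does not absorb it.

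**3. Follow-up.** End of Study is EoT + 28 days (+7): Day 1079 to 1086, weeks 154 to 155. That is before the week-156 visit which the premature-stop path asks the same patient to attend. (A patient who intends to use nintedanib outside the trial goes straight to End of Study instead.)

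**4. SAP visit windows.** SAP Table 6.7: 1 allocates Days 1038 to 1135 to the 156-week visit. Day 1051 lies inside. The same patient could supply 156-week laboratory and vital-sign data while being counted as premature.

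**5. Event or censored.** In SAP Table 5.4.3: 1, rule 3 censors at last intake a patient who has ended trial drug and has no documented event. If the protocol's time rule decides what an event is, the affected patient has one and rule 3 does not apply.

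**6. Who is affected.** Roll-over patients still on treatment, not leaving under the age-21 exception, whose own week 156 falls after the common EoT. Those already past week 156 are not affected.

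**7. How many.** The protocol expects at least 30 roll-over patients (Section 7.5). Their entry span W is not given. Assume uniform entry over W weeks, all 30 still on treatment, and a common EoT t weeks before the last Visit 15. Affected = 30 × t / W.

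| Entry span W (weeks) | t = 2 | t = 4 | t = 6 |
|---|---|---|---|
| 13 | 4.6 (15%) | 9.2 (31%) | 13.8 (46%) |
| 26 | 2.3 (8%) | 4.6 (15%) | 6.9 (23%) |
| 52 | 1.2 (4%) | 2.3 (8%) | 3.5 (12%) |
| 78 | 0.8 (3%) | 1.5 (5%) | 2.3 (8%) |

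**8. What it does to the outputs (illustration).** Suppose 6 of 30 stop for true reasons before week 150: 6/30 = 20%. Three administrative stops make it 9/30 = 30%. In the Kaplan-Meier analysis, with no earlier censoring, the proportion still on treatment is 24/30 = 0.80 at week 150, so the first quartile is not reached by then. After two administrative stops it is 22/30 = 0.73, below 0.75, and the first quartile is reported at weeks 150 to 156.

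**The case against.** The strongest reply is that the protocol's intent is clear from context. The common EoT is described as the planned end of treatment. The patients concerned go into the 4-week follow-up and not onto the path for premature stops. Premature stopping is tied in the same section to a withdrawal reason, and Section 6.2.3 places trial completion at End of Study for those who finish on treatment as planned. On that reading nobody would code these patients as premature, and SAP rule 3 would censor them without further instruction. The disposition table also shows reasons, so an administrative stop could be recognised.

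Much of this stands as evidence of intent. It does not remove the explicit time rule, which names its one exception and omits this case. Whether rule 3 applies depends on how the case report form codes the stop, which the documents do not show. So it is not established that these stops will be recorded as events, only that the stated rule makes them so.

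It is also fair that the early common EoT is optional, that up to 6 weeks is a ceiling, and that the curve before week 150 is untouched.

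**Conclusion.** The point holds as a defect in a stated rule, limited to disposition and time to premature treatment discontinuation. The counts are upper bounds: they rest on an assumed entry span, uniform entry, 30 roll-over patients and no losses or age-21 exits over about 3 years. The 46% figure belongs to the shortest span assumed with the full 6 weeks used. It is not an estimate for this trial.

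Two stronger readings are tempting, and the documents support neither.

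- A reader might infer that Sections 3.1 and 6.2.2 contradict each other on stops after week 156. They do not: one defines stops before week 156 as premature, and the other exempts one reason after it. The text is incomplete. The exemption would be needed only if other late stops counted as early, yet no current passage says whether they do. The completion list in Section 6.2.3 has no line for a roll-over patient who stops after week 156 for another reason, beyond its default of last contact.
- A reader might infer that the main safety result is distorted. It is not. The primary endpoint counts treatment-emergent adverse events up to 28 days after the last dose and does not use this label.

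The correction should be made before database lock, so that no patient has to be reclassified after the data are seen.

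**What to change.** Add one sentence to Protocol Section 3.1 and to SAP Sections 5.4.3 and 7.1, for example:

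> *A patient who stops trial medication at the sponsor-scheduled common EoT has completed treatment as planned, and is censored at last trial drug intake in the analysis of time to premature treatment discontinuation.*

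Under this rule no roll-over patient is premature for that reason, whatever the entry span.

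As a minor clarification, state how a roll-over stop after week 156 for a reason other than outside availability is classified, and use the same rule in Sections 3.1, 6.2.2 and 6.2.3. The two follow-up paths in Section 3.1 (4 weeks for all remaining patients; visits up to the individual week 156 for premature stops) should be reconciled in the same edit.

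The cost is a sentence or two in each document and one flag in the disposition dataset. The change concerns classification only; no new data are needed.
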